9.1.6 Product Complaints

A product complaint is defined as any written, electronic or oral communication that alleges deficiencies related to the identity, labeling, quality, durability, reliability, safety, effectiveness, or performance of a device (i.e., stapler) after it is released for distribution (policy of Johnson and Johnson Medical Device Quality management). A product complaint may or may not be associated with an AE/SAE.

9.2 REPORTING PROCEDURES FOR ADVERSE EVENTS/PRODUCT COMPLAINTS

9.2.1 REPORTING ADVERSE EVENTS

Data related to AEs will be recorded in the source documentation from the time of study enrollment (first incision) until the subject completes the study or terminates early. All AEs that are unresolved at study completion (or early termination) will be recorded as ongoing at study end.

Data related to SAEs will be collected until event resolution, or until the event is considered stable, or until all attempts to determine the resolution of the event are exhausted.

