4.4 REMOVAL OF SUBJECTS FROM STUDY

A subject has the right to withdraw from the study at any time for any reason without prejudice to his/her future medical care by the physician or the institution. Should a subject (or subject's legally authorized guardian/representative) decide to withdraw; all efforts will be made to collect and report the final visit observations as thoroughly and timely as possible.

Subjects who withdraw from the study prior to randomization will be considered screen failures and will be replaced. Subjects who withdraw from the study post-randomization will not be replaced. Subject participation may be terminated prior to completing the study for any of the reasons listed below. When a subject's participation is terminated prior to completing the study, the reason for withdrawal is to be documented on the Study Completion eCRF as well as in the source documentation:

Withdrawal of Consent:

The subject withdraws consent for participation in the study. Any method of contact with the subject in which they state they no longer want to participate in the study specific activities constitutes withdrawal of consent. When possible, the reason for withdrawal of consent will be documented.

Surgical:

The Investigator must withdraw a subject intra-operatively for the following reasons:

- Lobectomy not completed;

- Conversion to an open procedure, unless directly related to transection of the PA/PV (subject will be followed for safety up to 30 days post-op); or
- Use of robotic assistance during surgery.

Adverse Event:

When the subject experiences an adverse event and the Principal Investigator or Medical Director believes it is in their best interest to discontinue participation in the study, they will be withdrawn.

Death:

When possible, the cause of death will be documented.

Lost to follow-up:

When contact with the subject has been lost without completing a final visit assessment, and every attempt to contact has failed, the subject will be considered lost to follow-up. Final documentation regarding all attempts to contact the subject requesting their return for the final visit should be documented.

Site Termination or Study Termination:

A site or study may be terminated. When this occurs all subjects at the site will be withdrawn and documented as early termination. Reasons for site or study termination may include, but are not limited to the following:

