7.3 ANALYSIS SETS

There will be three analysis sets defined:

- The Full Analysis Set (FAS) will consist of all randomized subjects who had the procedure performed and provide data on number of surgical interventions;
- The Per Protocol (PP) Analysis Set will consist of all subjects in the FAS who had no major protocol violations;
- The Safety Set consists of all randomized subjects on whom the procedure is started.

The primary performance endpoint analysis will be performed on the Full Analysis Set and subjects will be classified according to their randomized treatment group. The primary performance endpoint analysis will also be performed on the PP set as a sensitivity analysis to the results on the FAS. The summary of additional endpoints will also be performed on the Full Analysis Set. Analysis of the primary safety endpoint and adverse events summaries will be performed on the Safety Set.

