Number of Vessel Transections Requiring Intervention [1] n (%)	xx (xx.x%) xx.x%, xx.x%	xx (xx.x%) xx.x%, xx.x%	xx (xx.x%) xx.x%, xx.x%
95% Confidence Interval for Percent			
Difference (95% CI) for Percent Requiring Transection [2]		xx.x% (xx.x%, xx.x%)	
Type of Intervention, n (%) [3]			
Additional Stapling	xx (xx.x%)	xx (xx.x%)	xx (xx.x%)
Over-sewing	xx (xx.x%)	xx (xx.x%)	xx (xx.x%)
Compression	xx (xx.x%)	xx (xx.x%)	xx (xx.x%)
Use of Suture	xx (xx.x%)	xx (xx.x%)	xx (xx.x%)
Sealant	xx (xx.x%)	xx (xx.x%)	xx (xx.x%)
Buttress	xx (xx.x%)	xx (xx.x%)	xx (xx.x%)
Use of Energy	xx (xx.x%)	xx (xx.x%)	xx (xx.x%)
Clip Placement	xx (xx.x%)	xx (xx.x%)	xx (xx.x%)
Blood Product Transfusion	xx (xx.x%)	xx (xx.x%)	xx (xx.x%)
Additional Surgical Procedure	xx (xx.x%)	xx (xx.x%)	xx (xx.x%)
Other Intervention	xx (xx.x%)	xx (xx.x%)	xx (xx.x%)

[1] Denominator for calculation of percentage is the total number of vessels transected in that group.

[2] Difference is calculated as Powered Vascular Stapler minus Standard of Care Stapler.

[3] Denominator for calculation of percentage is the total number of vessels requiring intervention in that group.

Table 7
Post-Operative Interventions or Procedures Related to Pulmonary Artery or Pulmonary Vein Bleeding
Safety Set

Characteristics	Standard of Care Stapler (N = ##)	Powered Vascular Stapler (N = ##)	Overall (N = ##)
Number of Subjects Requiring Post-Operative Intervention Related to Pulmonary Artery or Pulmonary Vein Bleeding			
n (%) [1]	xx (xx.x%)	xx (xx.x%)	xx (xx.x%)
95% Confidence Interval for Percent	xx.x%, xx.x%	xx.x%, xx.x%	xx.x%, xx.x%
Type of Intervention, n (%) [2]			
Blood Product Transfusion	xx (xx.x%)	xx (xx.x%)	xx (xx.x%)
Additional Surgical Procedure	xx (xx.x%)	xx (xx.x%)	xx (xx.x%)
Other Intervention	xx (xx.x%)	xx (xx.x%)	xx (xx.x%)

[1] Denominator for calculation of percentage is the total number of subjects in that group.

[2] Denominator for calculation of percentage is the total number of subjects requiring intervention in that group.

Table 8
Device Usage Details
Full Analysis Set

Characteristics	Standard of Care Stapler (N = ##)	Powered Vascular Stapler (N = ##)	Overall (N = ##)
Number of Subjects Where Device Was Articulated	xxx	xxx	xxx
Did Articulation Make it Easier to Perform Surgery? [1]			
Yes	xx (xx.x%)	xx (xx.x%)	xx (xx.x%)
No	xx (xx.x%)	xx (xx.x%)	xx (xx.x%)
Was Articulation Essential to Performing the Surgery? [1]			
Yes	xx (xx.x%)	xx (xx.x%)	xx (xx.x%)
No	xx (xx.x%)	xx (xx.x%)	xx (xx.x%)

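### Safety recording can stop at a mandatory intra-operative withdrawal while the subject stays in the Safety Set denominator, so post-operative intervention and AE rates may be understated

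*Protocol*

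**What the plan says.** Protocol 9.2.1 records adverse events "from the time of study enrollment (first incision) until the subject completes the study or terminates early". Events still open at that point are not pursued: "All AEs that are unresolved at study completion (or early termination) will be recorded as ongoing at study end". Serious events get more: "Data related to SAEs will be collected until event resolution, or until the event is considered stable", or until attempts to establish resolution are exhausted. Nothing says that new serious events are looked for after withdrawal.

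Protocol 4.4, under Surgical, states: "The Investigator must withdraw a subject intra-operatively for the following reasons". It lists three: the lobectomy is not finished, the operation is converted to open (with an exception for conversions directly related to PA/PV transection), or robotic assistance is used. Surgical withdrawal is one of the listed ways in which participation ends before study completion, so these subjects have terminated early. The conversion item adds in brackets "subject will be followed for safety up to 30 days post-op". The other two items carry no such note, nor does the paragraph on withdrawal for an adverse event. The promise in 4.4 to gather final-visit observations is attached to subjects who themselves decide to leave.

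On the analysis side, Protocol 7.3 says: "The Safety Set consists of all randomized subjects on whom the procedure is started". SAP section 7 agrees, and both use this set for the primary safety endpoint and the AE summaries. Footnote 1 of SAP Table 7 reads: "Denominator for calculation of percentage is the total number of subjects in that group". SAP 10.4 builds one record per subject with a yes/no indicator of a post-operative intervention. SAP 10.6 and Protocol 7.5.1 restrict summaries to observed data and rule out imputation.

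**The concern.** Read together, these rules allow a subject to leave safety observation in the operating room, before Visit 3 begins, and still be counted in the denominator of the primary safety endpoint and of the AE tables. An event that is never recorded lowers a rate whose denominator does not shrink with it.

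The loss need not be random. An unfinished lobectomy or a conversion may mark a difficult operation, and some of these subjects may already have a study staple line on a pulmonary vessel. The study is open-label and the surgeon judges whether a conversion is directly related to transection, so the loss can differ between arms. The point concerns post-operative safety ascertainment only. It does not concern who enters the Full Analysis Set.

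**Working it through.** **The plan's own figure.** The documents give no withdrawal share, post-operative bleeding rate or AE rate. Their only precision figure is a 95% margin of at most 2.9% per group for intra-operative interventions. It reproduces: 1.96 × √(0.06 × 0.94 / 260) = 2.887%. It has no bearing on this point.

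**Who is followed, as written.** Every row is in the Safety Set once the randomized subject's procedure has started.

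| Reason for exit (Protocol 4.4) | Safety follow-up stated |
|---|---|
| Conversion directly related to PA/PV transection | Exempt from withdrawal |
| Other conversion | Up to 30 days if the bracket refers to withdrawn conversions; none if it refers to the excepted ones |
| Lobectomy not finished | None |
| Robotic assistance | None |
| Withdrawal for an adverse event | None |
| Subject's own decision | Effort to obtain final-visit observations |

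**How the unobserved are counted.** The SAP supports two answers for Table 7:

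- If the indicator is set to 0, the denominator agrees with the Table 7 footnote, but an unobserved course is treated as event-free, contrary to 10.6.
- If the indicator is left missing, 10.6 is respected. The PROC FREQ code in 10.4 has no MISSING option and drops the record, so the denominator no longer matches the footnote.

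The AE shells are headed by the Safety Set N and state no other denominator.

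**Size under the full denominator.** Let w be the share of the Safety Set that is unobserved, p the rate in followed subjects, and r the ratio of the rate in unobserved to that in followed subjects.

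- Reported rate = (1 − w)p
- True rate = (1 − w)p + w·r·p
- Relative understatement = w·r / [(1 − w) + w·r], which equals w when r = 1

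All values of w and r below are assumptions.

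| w | r = 1 | r = 2 | r = 3 |
|---|---|---|---|
| 2% | 2.0% | 3.9% | 5.8% |
| 5% | 5.0% | 9.5% | 13.6% |
| 10% | 10.0% | 18.2% | 25.0% |
| 15% | 15.0% | 26.1% | 34.6% |

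For example, w = 15% and r = 3 give 0.45 / (0.85 + 0.45) = 34.6%. With r = 0, or if the subjects are in fact followed, there is no understatement.

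In absolute terms, with w = 10% and r = 3:

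- p = 2%: 1.8% reported against 1.8% + 0.6% = 2.4%.
- p = 30% (an assumed AE rate): 27% reported against 36%.

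For Table 7, a subject with no PA/PV transection cannot have the event. There r is the share of unobserved subjects who had a transection times the risk ratio among those subjects, so it may be below 1.

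**Difference between arms.** Suppose 10% of the powered vascular stapler (PVS) arm and 4% of the standard-of-care arm are unobserved, with equal true rates and r = 1. At a true 5%, the reported rates are 4.5% and 4.8%, a spurious −0.3 points. At 30% they are 27.0% and 28.8%, or −1.8 points. Both favour PVS.

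**Does an observed-only denominator cure it?** In the case p = 2%, w = 10%, r = 3, with 100 per arm, it gives 1.8/90 = 2.0% against a true 2.4%. That is still (2.4 − 2.0)/2.4 = 17% low. It removes the dilution but not the bias from informative loss.

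**The case against.** The other side has a good deal to say.

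- **Counting.** No passage says that unobserved subjects are counted as event-free. That follows from a footnote in a table shell, and the observed-data rule points the other way. This stands: the documents are in conflict, and neither reading can be called the plan's intention.
- **Numbers.** SAP section 3 told sites to randomize as close as possible to vessel transection in order to limit randomized drop-outs. Operations abandoned or converted before randomization never enter the Safety Set. This stands, and the unobserved share may be near the low end of the range. Late randomization also makes it likelier that a subject withdrawn afterwards has a staple line.
- **Who is lost.** Conversions directly related to PA/PV transection, the group closest to the endpoint, are not withdrawn, and other conversions may have 30-day follow-up. Subjects without a transection properly contribute no primary safety event. The documents do not describe robotic assistance as a complication. All of this narrows the gap. It does not close it for unfinished lobectomy, robotic assistance or AE withdrawals.
- **Serious events.** Protocol 9.2.2 triggers SAE reporting when the site becomes aware, with no stated cut-off, so a reoperation for bleeding might still be reported. Whether new SAEs after withdrawal are covered is unclear rather than excluded. Events before withdrawal are recorded in any case.
- **Consequence.** The safety endpoint is descriptive and has no acceptance limit. At p = 2% the assumed errors run from 0.04 to 0.9 points, small beside an exact 95% interval of about 0.2% to 7.0% for 2/100. SAP Table 1 shows surgical discontinuations by arm, so an imbalance would be visible. This limits the weight of the point, though Table 1 does not show who had post-operative data.

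**Conclusion.** The point holds as a possibility, not as demonstrated bias. The stated rules can lose post-operative events while keeping the subjects in the denominator, and the SAP contradicts itself on how they are counted. Post-operative PA/PV intervention rates (through subjects who had a transection) and AE rates may be understated, possibly unequally between arms.

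The size is unknown. On assumed inputs the relative understatement runs from 2% to 15% at equal risk, to about 35% at the extreme (15% unobserved, three times the risk), and is zero if the subjects are in fact followed or have no events.

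A reader might infer three stronger things that the documents do not support:

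- That every subject withdrawn in theatre is unfollowed and scored as event-free, so that all safety tables are certainly biased. The bracket on conversions, the SAE provisions and SAP 10.6 all prevent that conclusion.
- That 10 or 15 withdrawals per 100, or a raised risk among them, is expected. No passage gives such figures, and the plan's 6% is an intra-operative rate per firing.
- That the 3% acceptance criterion is affected. It applies to the intra-operative performance endpoint only.

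**What to change.** **Protocol 4.4 and 9.2.1.** Separate withdrawal from study activities from the end of safety data collection. Every randomized subject whose procedure has started, unless consent is withdrawn, should have AEs and post-operative PA/PV interventions recorded to one common end point, by telephone or from the chart. State which conversions the bracketed follow-up covers. Reconcile the 4-week visit with the 30-day note, and both with SAP section 4, which places collection of the primary safety endpoint through hospital discharge.

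**SAP Table 7 and 10.6.** Reconcile the footnote with the observed-data rule. Report by arm the number with post-operative data, and give the rate on that number and on the full Safety Set N. State how many of the unobserved had a PA/PV transection. The observed-only rate should accompany the continued follow-up, not replace it, because it does not remove bias from informative loss.

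**Cost.** Some wording, a few extra contacts or chart checks (Visit 4 may already be done by telephone), and a few more table rows. If follow-up has already ended, the SAP part can still be done.

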9.2.2 Reporting Serious Adverse Events

The site must complete the SAE eCRF within 24 hours of becoming aware of the event.

Supporting SAE documentation can be faxed to:

US sites:

[contact]
Study Number: ESC-15-001

EU sites:

Fax: [name]
Study Number: ESC-15-001

The Investigator will also be required to assess if the SAE is considered anticipated (see Appendix I) and if the event involved a product complaint. The report of an SAE by a study site does not constitute an admission that study personnel or the user facility (hospital/clinic) caused or contributed to the event.

The study site is also responsible for submitting to the reviewing IRB/EC according to their IRB/EC procedures.

9.2.3 Reporting Product Complaints

All product complaints related to powered vascular stapler shall be documented throughout the clinical investigation.

Product complaints related to powered vascular stapler must be reported to the Sponsor in a timely manner and no later than 24 hours after becoming aware of the event. The Product Complaint Form must be emailed to the EES Customer Complaint team at the following email address:

[contact]

One copy of the processed form should be kept on-site and the device should be retained. EES representatives will organize collection of the device for evaluation as needed.

11.0 APPENDIX I: ANTICIPATED ADVERSE EVENTS

Associated with Surgery and General Anesthesia	Thoracic Surgery Specific
Acute Lung Injury	Air/Gas Embolism
Acute Respiratory Distress Syndrome	Angina
Adhesions	Broncho pleural fistula
Altered Mental Status	Chylothorax
Anaphylaxis	Diaphragmatic Injury
Anemia	Empyema
Angina	Esophageal Injury
Atelectasis	Hemothorax
Bacteremia	Hernia
Bleeding	Intercostal nerve injury
Bradycardia	Pneumothorax
Cardiac Arrhythmia	Prolonged Air Leak
Central line infection	Thoracic duct injury
Cerebrovascular Accident / Stroke	Thromboembolic Event
Congestive Heart Failure	Wound infection
Constipation	Tightness of the chest
Death	
Deep Venous Thrombosis	
Dehydration	
Dementia	
Diarrhea	
DIC, Coagulopathy	
Dizziness	
Electrolyte Imbalance	
Fever, Pyrexia	
Headache	
Hematuria	
Hypertension	
Hypotension, shock	
Hypoxia	
Ileus	
Infection/SSI/Abscess	
Jaundice	
Lethargy	
Leukocytosis	
Liver Failure	

Mesenteric Infarct	
Mesenteric Ischemia	
Myocardial Infarction	
Nausea	
Obtundation, Depressed Level of Consciousness	
Oliguria	
Pain (increased/severe/chronic)	
Pneumonia	
Pulmonary Embolism	
Renal Failure	
Respiratory Failure	
Respiratory Insufficiency	
Sepsis	
Somnolence	
Systemic Inflammatory Response Syndrome	
Tachycardia	
Thrombocytopenia	
Thromboembolic Event	
Thrombosis	
TIA	
Tightness of the chest, Angina	
Tinnitus	
Urinary Retention	
Urinary Tract Infection (UTI)	
Volume Depletion, Hypovolemia	
Vomiting	
Wheezing	
Wound Dehiscence

This is the Statistical Analysis Plan (SAP) for the final analysis of data collected under Protocol ESC-15-001. This SAP describes in detail the statistical methodology and statistical analyses for the above mentioned protocol.

1 Study Overview

1.1 Study Objectives

The primary objective of the study is to demonstrate that the frequency of hemostatic interventions/procedures required intra-operatively or post-operatively related to the transection of the pulmonary artery (PA) and pulmonary vein (PV) during VATS lobectomy with the ECHELON FLEX™ Powered Vascular Stapler (PVS) is not increased when compared to standard of care (SOC) during video-assisted thoracoscopic surgery (VATS) lobectomy.

1.2 Study Design

This is a prospective, randomized, controlled, multi-center, open-label study that will collect and compare data from the surgeon's current SOC stapler (for PA/PV transection) and PVS. Prospective subjects will be informed about the nature of the research, given the informed consent document (ICD) to read, and if the subject understands the consent, will be asked to provide written consent.

2 Treatment Assignment

Subjects were assigned to either the surgeon's current SOC stapler or PVS. The ECHELON FLEX™ PVS with Advanced Placement Tip is a sterile, single use instrument that simultaneously cuts and staples tissue. There are four staggered rows of staples, two on either side of the cut line. The ECHELON FLEX™ PVS with Advanced Placement Tip and reloads have a staple line that is approximately 35mm long and a cut line that is approximately 30 mm long. The shaft can rotate freely in both directions and an articulation mechanism enables the distal portion of the shaft to pivot to facilitate lateral access to the operative site. The powered vascular stapler has been cleared for marketing by the FDA and is CE marked which allows for commercial distribution in the European Union. The device will be used in accordance with its product labeling and Instructions for Use.

3 Randomization and Blinding Procedures

Subjects were randomized to either the surgeon's current SOC stapler or PVS in a 1:1 ratio. Randomization could occur at any time prior to surgery up to transection of the vessel(s). Sites were instructed to wait until as close as possible to the actual time of vessel transection so as to minimize randomized drops within the study.

Randomization was accomplished through utilization of envelopes at the study site. Randomization envelopes were created according to the “Work Instructions for the Creation of Randomization Envelopes”, document number WE001625, based on a randomization schedule generated by the Ethicon Biostatistics group. The randomization schedule was generated using a validated program that incorporated variable block sizes and treatment assignment was balanced within each study site. This was an open-label study and therefore no blinding procedures were required.

4 Interval Windows

Interval windows are not defined for the purpose of analysis in this study as the collection of data for the primary performance endpoint occurs intra-operatively and the collection of data for the primary safety endpoint occurs through hospital discharge. The final visit occurred approximately 4 weeks after surgery, thus no interval windows need to be defined given the absence of long-term follow-up in this study. The complete Schedule of Events for this study can be found in the Synopsis of the study protocol.

5 Primary and Secondary Endpoints

5.1 Primary Performance Endpoint

The primary performance (effectiveness) endpoint in this study was defined as the occurrence of hemostatic interventions/procedures completed for intra-operative bleeding related to the transection of the PA and PV during VATS lobectomy with the use of either the SOC or PVS stapler. Hemostasis interventions or procedures were defined as bleeding detected and controlled intra-operatively (additional stapling, over-sewing, clip placement, compression, use of suture, sealant, and/or buttress, and/or use of energy); or bleeding that occurred intra-operatively requiring blood or blood product transfusion or an additional surgical procedure (e.g. conversion to open). No hemostasis intervention was defined as no bleeding at the staple line or bleeding that stopped after initial blotting of the staple line.

The primary performance endpoint will be summarized at the firing level as multiple firings per subject were expected and observed; that is, the denominator for the primary endpoint will be the total number of firings and the numerator will be the number of firings where an intervention was required.

During development of the protocol with the Notified Body (TUV) following their decision to grant CE mark to the device, a formal hypothesis was not defined for the study; however, to establish that the intervention rate of PVS is not increased compared to SOC, an acceptance criterion was developed and a 95% confidence interval for the difference in proportion of firings requiring interventions for PVS minus SOC will be calculated. The powered vascular stapler will be considered to have acceptable performance if the upper bound of the 95% confidence interval does not exceed 3%.

